## 1 BACKGROUND INFORMATION AND RATIONALE

### 1.1 Main RCT

Early childhood is a critical period in which young children attain developmental milestones necessary for cognitive, motor, language, and socio-emotional functioning. Unfortunately, developmental delays are commonly encountered among children under the age of 3 years. These delays occur when a child does not reach important milestones, e.g. independent ambulation, within an expected period of time in one or more domains. Twelve to sixteen percent of young children are estimated to have developmental delays or disorders.

Although developmental delays have been associated with a number of medical and genetic conditions, most are idiopathic and do not possess phenotypic characteristics that allow for easy recognition. As such, developmental delays when not identified early contribute to social and emotional problems and result in poor educational and functional outcomes. Lifetime costs for individuals with developmental disabilities has been estimated to exceed \$60 billion in 2003 U.S. dollars.

Identifying developmental delays and instituting early intervention (EI) services in a timely fashion are of critical importance to optimize child wellbeing. The EI Program (Part C of the Individuals with Disabilities Education Act) was established by Congress in 1986 to provide funding for states to establish and maintain programs of services to meet the needs of children with developmental delays and disabilities and their families. The evidence base for the effectiveness of EI services has been established. At-risk children without the benefit of early intervention services experience average declines in cognitive development of approximately 0.5-0.75 SD units. EI systems have been found to prevent or reduce cognitive declines in at-risk children in the first five years of life and to mitigate stressors among at-risk families that contribute to developmental delays. Reviews of EI programs found average improvements of 0.43-0.75 SD (~8-12 IQ points) in cognitive function. However, much of the research on the effectiveness of EI on at-risk children has involved premature infants, so it isn't clear how effective EI services are for term or late preterm at-risk children.

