#### ***6.4.2.2 Specific Aim 2***

We will assess whether family engagement is a mediator of intervention treatment effects. We will address this aim by focusing on the role of family engagement using the EI Engagement questionnaire at 3, 6, 9, and 12 months as a mediator of the effect of the intervention on the study outcomes. Family engagement will occur post randomization and thus can be considered as a potential mediator as opposed to being a confounder. The response models discussed previously will be modified to include the EI Engagement questionnaire overall and domain scores as potential mediators in separate models to evaluate its mediating role in the association of interest. The association between outcome measures and the intervention conditional on the covariate will be compared to the marginal association estimated by the first aim.

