### **6.5 Sample Size, Statistical Power and Analysis Plan**

Our target sample size accounting for clustering by practice site for patients with complete 12-month follow-up is 300 participants. Assuming at least an 80% follow-up rate, the number needed to recruit to obtain this final sample size is about 360. Since a partial goal of the proposed intervention is to increase patient engagement, the rate of drop out is likely to be lower among the intervention group. If we conservatively assume that the drop-out rate among control patients is double that of patients on the intervention, the sample of patients

with complete follow-up will consist of approximately 130 control patients and 170 intervention patients.

Using the Bayley-III cognitive subscale as a primary outcome, we assert that the proposed intervention would be successful if it resulted in an increase of 3 points or more on this subscale. This is the minimal clinically significant outcome difference. Thus, based on the proposed sample size, we would obtain 96% power to detect a clinically meaningful difference in the Bayley-III cognitive scores. The power was estimated based on a simulation study that assumed that the sole impact of the intervention was on increasing enrollment into EI. Based on expected cognitive improvements due to EI found by Guralnick et al, we further assume that children who enrolled in EI had an average increase over a 12 month period of 10 points on the cognitive scale with a standard deviation of 1 point compared to patients who did not enroll. Based on these assumptions, an increase of 3 points on the cognitive scale between the intervention and control group would be the result of an increased rate of enrollment from 50% among controls to 80% among the intervention group. These rates of enrollment are consistent with rates suggested by our pilot data (Preliminary Studies Section).

**Figure 1** *Assessment of power to detect a clinically meaningful difference*

Power	n	
0.96	300	Assuming a minimal clinically significant outcome difference ( $\geq 3$ points increase in the BSID-III cognitive subscale)

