If this level of mediation by engagement and enrollment rates is replicated in the proposed trial, such differences should be adequately characterized by the proposed mediation analysis. To assess power to detect moderating effects, we use dichotomized literacy as an example based on having a SAHL score  $\leq 14$ . We assume a rate of inadequate literacy of 50% in each group and that the overall effect of the intervention on the cognitive score is the same as before. Using a simulation study based on these assumptions, the proposed sample size would give us approximately 84% power to a 6-point difference in differences for the effect of the intervention among children whose parents have inadequate literacy compared to children whose parents have adequate literacy.

**Figure 2** *Assessment of power to detect moderating effects*

Power	n	
0.84	300	Assuming a rate of inadequate literacy of 50% in each group and that the overall effect of the intervention on the cognitive score is the same as before.

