Analysis: Test the association between study arm at 3 months and EI referral completion and the association between EI parent engagement at 3 months (mediator) and EI referral completion. If both associations are significant, complete a mediation analysis of the association between study arm and completion of EI referrals, mediated by parent EI engagement.

- b. *Hypothesis 2b:* Completion of EI referrals and participation in EI services (dosage) will mediate the association between program participation (duration), parent engagement, and child developmental status

Analysis of EI referral completion and child development status: Test the association between EI engagement at 3 months and Bayley language & cognitive T scores and the association between MDE completion (mediator) and EI engagement at 3 months. If both associations are significant, complete a mediation analysis of the association between EI engagement at 3 months and Bayley language and cognitive T scores, mediated by EI referral completion.

Analysis of program participation and child development scores: Test the association between program participation and Bayley language & cognitive T scores and the association between referral completion (mediator) and program participation. If both associations are significant,

ODEI Study Statistical Analyses Plan

complete a mediation analysis of the association between program duration and Bayley language and cognitive T scores, mediated by referral completion.

Variable Definitions:

- Program participation: participation in ODEI intervention
- Completion of EI Referrals: Completion of Multidisciplinary Evaluation (MDE)
- Initiating EI services: Date of first early intervention service
- Duration of EI services: The time between the EI service initiation and discharge from early intervention OR 12 months from randomization (if discharge date is unavailable)
- Developmental outcomes: Language and cognitive composite scores from BSID III assessment.
- Parent engagement: total score from 2 subscales on parent engagement (Buy-In/Receptivity to EI and Advocacy/Navigating the EI Process)

Aim 3: To explore whether the home learning environment, parental health literacy, or poverty moderate the effects of the Opening Doors to Early Intervention Program on child developmental status.

a. *Aim 3a:* To explore whether differences in developmental scores between intervention and control groups varies by the richness of home learning environment

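### SAP Aim 2 runs each mediation analysis only after a significant total association, so the program-to-Bayley mechanism analysis could often be skipped even if the mechanism were exactly true

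*SAP*

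**What the plan says.** SAP Aim 2 sets out three mediation analyses, all conditional.

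- **Hypothesis 2a** (arm, engagement, referral completion). The pre-tests are arm with referral completion and 3-month engagement with referral completion. Then: "If both associations are significant, complete a mediation analysis of the association between study arm and completion of EI referrals", mediated by engagement.
- **Hypothesis 2b, engagement analysis.** The first pre-test reads "Test the association between EI engagement at 3 months and Bayley language & cognitive T scores"; the second is evaluation (MDE) completion with engagement. The same condition follows.
- **Hypothesis 2b, program analysis.** "Test the association between program participation and Bayley language & cognitive T scores and the association between referral completion (mediator) and program participation". If both are significant, the analyst is to "complete a mediation analysis of the association between program duration and Bayley language and cognitive T scores, mediated by referral completion".

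The exposure is program participation in the last pre-test but program duration in the analysis it gates, and the SAP does not define the latter. The 2b gates name two Bayley scores without saying whether each, either or both must reach significance.

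The protocol sets no such condition. Section 6.4.2.2, which covers mediation by engagement only, says: "The association between outcome measures and the intervention conditional on the covariate will be compared to the marginal association estimated by the first aim". Section 6.5 expects that, if mediation by engagement and enrolment is replicated, "such differences should be adequately characterized by the proposed mediation analysis".

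**The concern.** A mediated effect is made of two paths: exposure to mediator, and mediator to outcome given exposure. Neither requires the total exposure-outcome association to be significant. When an effect is diluted through a mediator that only some children gain, the total effect can be much harder to detect than its two components. Gating on it therefore tests something mediation does not need.

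The 2b program analysis is where this matters most, because it examines the mechanism on which the trial was sized: the power simulation "assumed that the sole impact of the intervention was on increasing enrollment into EI". If the Bayley comparison misses significance, the gate removes the analysis that would show whether completing the referral goes with better development. That is when readers most need it.

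**Working it through.** **Inputs.** From Protocol 6.5: uptake 50% (control) and 80% (intervention); +10 points from enrolment, SD 1; total effect 10 × 0.30 = 3 points; 130 and 170 completers; stated power 96%. From Protocol 1.1: "average improvements of 0.43-0.75 SD (~8-12 IQ points) in cognitive function".

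**Assumptions.** Two-sided alpha 0.05 (neither document states it); program participation means randomised arm; uptake stands in for MDE completion; an unadjusted comparison of a continuous score in completers; each score gated separately; no clustering.

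**Step 1: the plan's 96%.** The stated components alone give arm variances 100 × 0.25 + 0.5 = 25.5 and 100 × 0.16 + 0.8 = 16.8. The SE is √(25.5/130 + 16.8/170) = 0.543, and 3/0.543 = 5.52, which is 99.98% power. So 96% needs a larger SD that is not stated: 3 / [(1.960 + 1.751) × √(1/130 + 1/170)] = 3 / (3.711 × 0.1165) = 6.94.

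**Step 2: other SDs in the documents.** Section 1.1 gives 12/0.75 = 16.0 and 8/0.43 = 18.6. These are rounded IQ-point figures from reviews, used here as a range.

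**Step 3: power of the total-effect pre-test.** Power = Φ(3/(SD × 0.1165) − 1.960).

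- SD 6.94: Φ(1.75) = 0.960
- SD 16: Φ(−0.35) = 0.363
- SD 18.6: Φ(−0.58) = 0.282

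The arm-to-mediator pre-test (50% against 80%) has 99.98% power, so the skip rate is essentially one minus the total-effect power.

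**Step 4: the ungated paths.** Within-arm variance due to uptake is about 20.6, so the residual SDs at total SD 16 and 18.6 are √(256 − 20.6) = 15.34 and √(346 − 20.6) = 18.04. The within-arm sum of squares of the mediator is 129 × 0.25 + 169 × 0.16 = 59.3, with root 7.70. The SEs of the mediator coefficient are 15.34/7.70 = 1.99 and 18.04/7.70 = 2.34. Against 10 points these give ratios of 5.0 and 4.3, or power of about 99.9% and 98.9%.

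**Step 5: simulation of the full gate**, in two independent runs (10,000 and 20,000 trials per SD):

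| Total SD | Gate skips | Joint test of both paths succeeds |
|---|---|---|
| 6.9 | 4.3% | above 99.9% |
| 16 | 63–64% | 99.8–99.9% |
| 18.6 | 71–72% | 98.8–98.9% |

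**Step 6: sensitivity.**

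- *Two scores* (same effect on language, residual correlation 0.5–0.7, both assumed). If either score suffices, the gate skips about 2% at SD 6.9 and 50–62% at SD 16–18.6. If both are required, about 7% and 76–85%.
- *MDE completion as a weaker proxy.* If 30% of non-enrolled children also complete it, skip is 65–72% and joint power 95–88% at SD 16–18.6. If 50% do, 66–73% and 79–69%.
- *When the gate is passed* at SD 16–18.6, the mean indirect estimate is 3.14 and 3.12 (true value 3). The mean direct estimate is 1.79 and 2.46 (true value 0), falsely significant in 7.4% and 9.6% of those trials.

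**Step 7: the other gates.** In 2a the arm-to-referral test compares 50% with 80%, for power above 99.9%. Under the weaker proxies the rates are 0.5 + 0.3 × 0.5 = 65% against 86%, or 75% against 90%, with power of about 99% and 93%. That condition seldom skips anything. For the 2b engagement gate the documents give no engagement-Bayley association, so no skip rate can be computed.

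**The case against.** Several objections carry weight.

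- *This restates a question about primary power.* Largely true of the size. At the SD that 96% power implies the gate costs about 4%; the large figures arise only if the unstated SD is much bigger. What the gate adds is that a non-significant total effect also removes the mechanism analysis.
- *The pre-tests omit a component path, so a reader might infer that arm-to-engagement (2a) or referral-to-Bayley (2b) is never analysed.* The documents do not support that. A mediation analysis, once run, estimates those paths. The omission is a flaw of the gate, not a gap in the analysis.
- *Program participation may not mean arm.* The SAP says study arm in 2a, but in 2b it refers to participation in the intervention and adds duration. If actual participation is meant, the 130/170 contrast and the skip rates do not apply.
- *The test is not specified.* Aim 2 names no model, SAP Aim 1 names logistic regression for Bayley scores, the SAP calls the outcome both T scores and composite scores, and the protocol plans multiple imputation. The figures cover an unadjusted continuous comparison in completers.
- *Little is lost.* Aims 1a and 1c already report arm with MDE completion and arm with Bayley. A skip loses the mediator-to-Bayley path and the indirect estimate, which are the substance of Hypothesis 2b.
- *The protocol conflict is thin.* This stands. Section 6.4.2.2 is ungated but covers engagement only, so it contrasts with 2a rather than the 2b program analysis. The Section 6.5 remark is about power, and its silence on gating is weak evidence.

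**Conclusion.** The concern holds for the gating rule. All three mediation analyses depend on a significant total association that mediation does not require. Only the 2b program analysis has a demonstrated and potentially large cost: about 4% of trials skipped at SD 6.9, and about 63–72% at SD 16–18.6, for an effect whose two paths an ungated joint test would find in about 99% (69–95% with a weaker proxy). The skip rates rest on the assumptions listed above and on an outcome SD that the protocol does not give. The joint-test figures also assume no mediator-outcome confounding.

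A reader might infer that the analysis will probably be skipped, or that all three gates do similar harm. Neither follows: the SD is unknown, the arm-to-referral condition in 2a seldom bites, and the engagement gate cannot be quantified. Aim 2 is secondary and the primary result is unaffected. This should be changed because the change is cheap.

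**What to change.** Delete the three significance conditions in SAP Aim 2. For each hypothesis, fit the mediator model (exposure to mediator) and the outcome model (mediator plus exposure). Report indirect and direct effects with bootstrap 95% confidence intervals whatever the total-effect p-value, separately for the cognitive and language scores, labelled secondary. In the 2b program analysis use randomised arm as the exposure in both the association test and the mediation model, replacing the undefined program duration. Adjust for sex, age and primary care site, as in Aim 1, and for baseline engagement where collected (Protocol Table 1 and Section 5.1.2.1 schedule it at baseline). State that the mediator-outcome path is not randomised.

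The cost is SAP wording, modest analysis time and a few more secondary estimates to report. No new data are needed.

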## 1.5 Relevant Literature and Data

Child Find services are a mandated component of Part C of the Individuals with Disabilities Education Act to identify and enroll eligible children with developmental delays and disabilities. Child Find practices utilized by EI agencies may employ a variety of different strategies ranging from public awareness campaigns to developmental screening to childcare and clinician referrals. In previous studies, we found that only 50% of urban patients in Philadelphia completed EI referrals once they were identified as having delays and referred using these strategies (See Preliminary Studies section). However, none of these current practices seek to engage, inform, and assist parents to overcome motivational, knowledge, and practical barriers to completion of referrals.

This application is innovative, in our opinion, in adapting a PN model to address poor EI referral and service completion. This model termed “Opening Doors to Early Intervention” was based on a review of the literature of patient navigators (or family navigators, as we will refer to them in our study) and received practical input from practicing clinicians, EI staff, and parents to adapt it. The intervention was manualized to ensure consistency of procedures and included multiple modules addressing 1) education of families regarding knowledge of early child development, 2) information on the EI system and steps necessary to complete an EI referral, 3) brief motivation interviewing to assess families’ goals and treatment preferences and level of interest in initiating EI referrals, 4) assistance with overcoming barriers to completing EI referrals and maintaining EI enrollment, and 5) social work referral in the event of medical complexity or family crisis (See Appendix for Manual of Operations). PNs met with families soon after a referral was made and then followed up with families using phone, email, or text messaging to track completion of the referral steps leading to a multidisciplinary evaluation for services (Fig 3). PNs provided assistance and encouragement when families experienced barriers to the completion of steps. Although the referral steps shown here are county-specific, we retained flexibility in the manual to allow adaptation to counties with different referral processes and steps.

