ODEI Study Statistical Analyses Plan

Title: The Opening Doors to Early Intervention Study (ODEI)

NCT Number: NCT03625115

Document Date: July 3rd, 2024

ODEI Study Statistical Analyses Plan

Aim 1: To test the effectiveness of the Opening Doors to Early Intervention Program on EI service use and child developmental status among poor minority children residing in an urban community.

- a. *Hypothesis 1a:* A greater proportion of children who are randomized to the intervention will complete EI referrals than children in the control condition at 12 months.

Analysis: Chi square analysis on the difference in completion of MDE by study arm and logistic regression on the difference in MDE completion by arm, controlling for sex, age, and primary care site.

- b. *Hypothesis 1b:* Among children eligible for EI services, children randomized to the intervention will initiate EI services at a greater rate & receiving a longer duration of EI services than children in the control condition.

Analysis: Chi square test on the difference in EI service initiation by arm and logistic regression, controlled for sex, age, and primary care site. Survival analysis with a Kaplan-Meier curve of EI duration of services by arm.

- c. *Hypothesis 1c:* As a result, children who are randomized to the intervention will have more favorable developmental outcomes than children in the control condition at 12 months.

Analysis: Logistic regressions to determine the difference in cognitive and language BSID III scores by arm, controlling for sex, age, and primary care site.

Variable Definitions:

- Completion of EI Referrals: Completion of Multidisciplinary Evaluation (MDE)
- Initiating EI services: Date of first early intervention service
- Duration of EI services: The time between the EI service initiation and discharge from early intervention OR 12 months from randomization (if discharge date is unavailable)
- Developmental outcomes: Language and cognitive composite scores from BSID III assessment.

Aim 2: To assess whether parent engagement mediates the effects of the Opening Doors to Early Intervention Program.

- a. *Hypothesis 2a:* Parent engagement will mediate the association between program participation and completion of EI referrals and participation in EI services (duration).

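### SAP Aim 2b tests its gate on program participation but then mediates on an undefined program duration; study arm should be the exposure throughout (minor)

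*SAP*

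**What the plan says.** SAP Aim 2, Hypothesis 2b, states that referral completion and EI service use "will mediate the association between program participation (duration), parent engagement, and child developmental status". The second analysis under that hypothesis has two steps.

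- **Gate:** "Test the association between program participation and Bayley language & cognitive T scores and the association between referral completion (mediator) and program participation".
- **Mediation, if both tests are significant:** "complete a mediation analysis of the association between program duration and Bayley language and cognitive T scores, mediated by referral completion".

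The Aim 2 variable definitions include "Program participation: participation in ODEI intervention", which has no time component. The only duration they define is that of EI services: "Duration of EI services: The time between the EI service initiation and discharge from early intervention", or 12 months from randomisation if no discharge date is available. Program duration is not defined in the SAP or the protocol.

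Hypothesis 2a also starts from program participation: "Parent engagement will mediate the association between program participation and completion of EI referrals and participation in EI services (duration"). There the bracketed word belongs to EI services. Its analysis uses study arm in the first gate test and again in the mediation: "complete a mediation analysis of the association between study arm and completion of EI referrals, mediated by parent EI engagement".

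**The concern.** A gate licenses only the analysis whose exposure it tested. Here the exposure changes between the two steps, and the new one has no start, end, unit, source or control-arm value. The analyst would have to choose it, possibly with the data in hand.

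This analysis is the SAP's test of the path from navigation through EI referral to child development. The sample size section (Protocol 6.5) assumes that EI enrolment is the intervention's only route of effect, so readers will look to this analysis for the mechanism. An exposure that is not the randomised arm would lose the protection of randomisation on the exposure side of the path.

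**Working it through.** **Step 1: the exposure named at each step.**

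| Place | Exposure | Defined? |
|---|---|---|
| SAP 2a, mediation | study arm | yes, by randomisation |
| SAP 2b, hypothesis | program participation (duration) | label only |
| SAP 2b, both gate tests | program participation | yes, no time element |
| SAP 2b, mediation | program duration | no |
| Protocol 6.4.2.2 | the intervention (mediator: engagement) | yes |

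**Step 2: the possible readings.**

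1. *A slip for participation, meaning arm.* The mediation then matches its gate, and only the wording needs correcting.
2. *Time with the navigator.* This is observed after randomisation. Controls receive usual care (Protocol 7.1.1), so they have no natural value.
3. *Duration of EI services.* Protocol 1.5 has navigators "track completion of the referral steps leading to a multidisciplinary evaluation for services". Protocol 5.1.2.1 lists the MDE as the last referral step and then eligibility and service initiation. The SAP defines referral completion as MDE completion, so the proposed mediator would precede the exposure.

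**Step 3: how much reading 2 would change the result.** The documents give no figure, so this is an illustration.

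Inputs from the protocol:
- 170 intervention and 130 control completers, enrolment 80% against 50%, and 10 points from EI (6.5);
- outcome SD 12/0.75 = 16 (1.1).

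Assumptions:
- MDE completion stands for enrolment;
- controls are coded 0, and intervention contact has mean 12 months and SD 1 or 3;
- latent engagement has correlation r with contact length, with the latent variable behind MDE and with the part of the Bayley score not due to EI;
- contact length itself has no effect on MDE or Bayley.

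*Correlation of duration with arm.* With p = 170/300 = 0.567, p(1−p) = 0.2456, so 12√0.2456 = 5.947 and 144 × 0.2456 = 35.36. The correlation is 5.947/√(35.36 + SD² × 0.567).
- SD 3: 5.947/√40.46 = 0.935.
- SD 1: 5.947/√35.93 = 0.992.

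*Indirect effect at r = 0.*
- Arm: (0.80 − 0.50) × 10 = 3.0 points.
- Duration, per 12 months: (35.36 × 0.30/Var) × 10, which is 10.61/40.46 × 10 = 2.6 at SD 3 and 10.61/35.93 × 10 = 2.95 at SD 1.

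*Indirect effect at r = 0.5, arm as exposure.* The engagement gap between MDE completers and non-completers is r·φ(c)/[q(1−q)], where q is the MDE rate, c its normal cut-point and φ the normal density.
- Intervention: 0.5 × 0.2800/0.16 = 0.875.
- Control: 0.5 × 0.3989/0.25 = 0.798.
- Pooled with weights 170 × 0.16 = 27.2 and 130 × 0.25 = 32.5: 0.833.
- MDE-Bayley slope: 10 + 16 × 0.5 × 0.833 = 16.66.
- Indirect effect: 0.30 × 16.66 = 5.0, against a true 3.0.

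*Indirect effect at r = 0.5, duration as exposure (simulated).* About 4.7 at SD 3 and 5.1 at SD 1.

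So at SD 3 the choice between arm and duration moves the estimate by 0.4 points (r = 0) or 0.3 points (r = 0.5). Engagement confounding of the MDE-Bayley link adds 2.0 points at r = 0.5 with arm as the exposure. Adding engagement itself to the outcome model brings the slope back to 10 and the indirect effect back to 3.0.

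**The case against.** The intended exposure can largely be recovered. The analysis is introduced as one of program participation, both gate tests use that defined term, and Aim 2a turns it into study arm. Protocol 1.4 has the navigator in contact throughout the study. Protocol 7.1.1 lets the frequency of contact vary with family preference but sets no family-specific length. As planned, then, navigator time is nearly constant in the intervention arm, and with controls at 0 it is close to arm on another scale. Writing arm also leaves engagement confounding of the MDE-Bayley link in place.

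All of this stands and limits the point to a minor one. It does not make the text adequate. Hypothesis 2b repeats the bracketed duration, so the wording is not confined to one sentence, and the SAP supplies no control-arm value.

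A reader might infer that the switch produces a high rate of false mediation findings. That would need contact length to vary freely with engagement and the analysis to be confined to the intervention arm. The documents plan neither. A reader might also infer that the SAP contradicts Protocol 6.4.2.2. That section does take the intervention as exposure, but its mediator is engagement, so it does not settle the exposure for mediation by referral completion.

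**Conclusion.** The point holds as a minor specification error. The gate and the mediation name different exposures, and the second is undefined. One alternative reading puts the exposure after randomisation with no control value; the other puts it after its own mediator. Only study arm gives the mediation that was gated.

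Under the navigator-time reading, the size is about 0.3 to 0.4 Bayley points in the indirect effect at an assumed SD of 3 months, and less at SD 1. Contact SD, control coding and r are all assumptions. The EI-services reading has no comparable figure, because there the ordering itself fails.

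Using arm makes the two steps agree and keeps a randomised exposure. It does not by itself make the indirect effect unconfounded. Nothing here reaches the primary comparison, which Protocol 6.3 keeps as randomised; a reader who inferred otherwise would be going beyond the documents.

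**What to change.** In SAP Aim 2b, replace program duration, program participation (duration) and the program participation named in the gate tests with randomised study arm, so that hypothesis, gate and mediation share one exposure. Adjust for sex, age and primary care site, as in Aim 1.

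Also add the baseline EI Engagement score to the mediator and outcome models, since arm alone leaves the MDE-Bayley link open to confounding by engagement. The score is already collected at baseline (Protocol Table 1). It will remove that confounding only as far as the questionnaire captures engagement, and the report should say so.

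The cost is a wording change to one conditional secondary analysis. No new data, visits, participants or protocol amendment are needed.
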